7.1 Sample Size Determination

This is a Phase 2 pilot study to determine feasibility and preliminary data for a larger study. Therefore, the proposed sample size is not necessarily expected to provide enough statistical power to see significant group differences.

7.2 Statistical Methods

PET images will be analyzed using 1) the two-tissue kinetic model to calculate total distribution volume, corrected for free fraction of radioligand in plasma (V_T/f_P), and 2) the cerebellum as a pseudo-reference region to calculate standardized uptake value ratios (SUVR). Effect size will be calculated for different regions as the difference in means (AD vs. controls) divided by the standard deviation.

We will also calculate test-retest reproducibility for ¹¹C-ER176 using data from the 4 controls who have two ¹¹C-ER176 scans.

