1.4.1.3. Brain imaging with ¹¹C-ER176 in human subjects

Eight separate healthy volunteers with either HAB, MAB, or LAB status had brain PET scans with 11 C-ER176 (1 man and 2 women each for HAB and MAB status and 2 men with LAB status; 32 ± 9 y old) [20]. TSPO affinity type was determined by in vitro receptor binding to TSPO on leukocyte membranes or genetic analysis. The 3 HABs who participated in the brain PET scans received an oral dose of 90 mg of the TSPO agonist N-benzyl-N-ethyl-2-(7-methyl-8-oxo-2-phenylpurin-9-yl)acetamide (XBD173) as a partial blockade about 1.75 h before the second injection of 11 C-ER176.

For brain images, total volume of distribution (V_T) , an index of receptor density that equals the ratio at equilibrium of the concentration of radioligand in tissue to that in plasma, was calculated with 1- and unconstrained 2-tissue compartment models (2TCM and 1TCM, respectively) using the radiometabolite-corrected plasma input function. To determine the minimal scan length for reliable measurements and also to indirectly assess whether ^{11}C -ER176

radiometabolites enter the brain, the time stability of V_T was examined by increasingly truncating the 90-min scan by 10-min increments to the shortest length of 0–50 min.

A modification of the Lassen plot was used to estimate V_{ND} of $^{11}\text{C-ER176}$ in brain in 2 ways: with an occupancy plot using the difference in V_T at baseline and after partial blockade with XBD173 in HABs, and with a polymorphism plot using the difference in V_T between 2 genetic groups (i.e., between HABs and MABs, between HABs and LABs, and between MABs and LABs).

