Brain time–activity curves fitted better with 2TCM than 1TCM. The unconstrained 2TCM fitting converged in brain time–activity curves from all regions, in all scans, and in all genotypes, both at baseline and after blockade with XBD173 in HABs (Fig. 4A). Compared with the 1TCM, the 2TCM showed lower mean Akaike information criterion scores (130 vs. 242) and higher mean model selection criterion scores (6.4 vs. 2.9). An F test also showed that the goodness of fit was significantly better with the 2TCM than with the 1TCM in all 154 fittings over a total of 11 scans, indicating the presence of significant amounts of both specific and nonspecific binding in human brain. The 2TCM identified V_T well, with an average SE of 2.4% across brain regions. Regional V_T values (mL·cm-3) were consistent with the known distribution of TSPO, showing high levels in the brain stem (4.3) and low levels in the putamen (3.2) at baseline for HABs.

After receiving XBD173, all 3 HABs showed marked blocking effects, both in brain and in plasma. That is, receptor blockade decreased peak uptake in brain, increased washout, and decreased total uptake over the 90-min scan (Fig. 1A). In plasma, XBD173 significantly increased the concentration of ¹¹C-ER176, consistent with its blocking the distribution of the radioligand to organs of the body (Fig. 1B)

[figure not shown]

Fig. 1. Brain uptake and plasma radioactivity concentrations (conc) of 11 C-ER176 in representative HAB at baseline (\circ) and after blockade with 90 mg of XBD173 (\bullet).

 V_T values were stable from 60 to 90 min and were well identified (SE < 10%) in all 3 genotypes with the exception of 1 MAB and in the 3 HABs after blockade, which had low specific binding like that in LABs, indicating negligible accumulation of radiometabolites regardless of the genotype.

 V_T values were higher for HABs than for LABs in all regions of interest, with intermediate values for MABs. The whole-brain V_T in HABs (3.3 \pm 0.9 mL·cm-3) was about 1.2-fold higher than that in MABs (2.9 \pm 0.9 mL·cm-3) and about 2.2-fold higher than that in LABs (1.6 \pm 0.5 mL·cm-3). V_T for 11 C-ER176 was well identified by the 2TCM in all genotypes.

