The receptor blocking study using XBD173 found that $^{11}\text{C-ER176}$ had adequately high BP_{ND} for all genotypes. The whole brain BP_{ND}—without correcting for f_P—was 4.2 ± 1.3 and 1.4 ± 0.8 for HABs and LABs, respectively. The high BP_{ND} and good identifiability in all genotypes, including LABs, suggests that this new radioligand would likely have better sensitivity in detecting abnormalities in patients and that LABs may not need to be excluded as they are for $^{11}\text{C-PBR28}$.

In summary, although ¹¹C-ER176 does not show sensitivity to the rs6971 SNP in vitro (see Section 8.1.1.), this radioligand does show a small degree of sensitivity to the SNP in vivo. This in vivo sensitivity is seen in both brain and peripheral organs (see Section 9.2.). However, the difference in binding between HABs and LABs is much lower for ¹¹C-ER176 than for ¹¹C-PBR28. Importantly, V_T and BP_{ND} may be reliably quantified in LABs with ¹¹C-ER176.

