Subjects will have genetic analysis to determine the presence of the rs6971 (Ala147Thr) SNP on the TSPO gene.

Target sample size for completers is 15 amyloid-positive patients and 15 amyloid-negative controls (30 subjects total). Our enrollment goal of 25 subjects per group will allow a 40% general screen failure/drop-out rate. Subjects who are coenrolled in other CUMC studies will not need to have brain MRI under this protocol if done within the last 12 months. Coenrolled subjects will not need to have ¹⁸F-florbetaben PET under this protocol if 1) they are controls and have had a negative ¹⁸F-florbetaben or other amyloid PET scan within the previous 12 months, or 2) they are patients and have ever had a positive amyloid PET scan using any amyloid radioligand (¹⁸F-florbetaben, ¹⁸F-florbetapir, ¹⁸F-flutemetamol, or ¹¹C-Pittsburgh Compound B).

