3.3 Secondary Study Endpoints

Coefficient of variation (%COV = standard deviation / mean) will be calculated for controls and patients with AD for both $V_{\rm T}/f_{\rm P}$ and SUVR data. SUVR values will be calculated using cerebellum as reference regions. Additional reference regions will be explored. Correlation coefficients will be computed to look for correlation between 11 C-ER176 binding and clinical severity. We will also look for correlations between 11 C-ER176 binding and atrophy, as

determined using ROI volumes derived from MRI data. We will also calculate test-retest reproducibility for ¹¹C-ER176 using data from the 4 controls who have two ¹¹C-ER176 scans.

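### The primary V_T/f_P effect size leaves out rs6971 genotype, which is collected for every subject and affects ER176 binding in vivo; adjusting for it costs almost nothing

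*Combined protocol and SAP*

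**What the plan says.** Sections 3.2 and 7.2 give two PET outcome measures. One is V_T/f_P, from "the two-tissue kinetic model to calculate total distribution volume, corrected for free fraction of radioligand in plasma". The other is SUVR with the cerebellum as pseudo-reference region. For both, the group comparison is: "Effect size will be calculated for different regions as the difference in means (AD vs. controls) divided by the standard deviation". Which SD is meant is not stated, and no covariate is named. Section 3.3 adds secondary analyses of tracer binding against clinical severity and atrophy: "Correlation coefficients will be computed to look for correlation between". It does not say which binding measure is used, and it has no genotype term.

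Genotype will be available. Section 3.1.1 states: "Subjects will have genetic analysis to determine the presence of the rs6971 (Ala147Thr) SNP on the TSPO gene". Section 6 accepts an earlier genotype result whatever its date. Section 4.2 has no genotype exclusion, and section 1.4.1.3 suggests that low-affinity binders (LABs) may not need to be excluded with this tracer.

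Section 1.4.1.3 reports that whole-brain V_T in high-affinity binders (HABs) was about 1.2-fold that in mixed-affinity binders (MABs) and "about 2.2-fold higher than that in LABs". It sums this up by saying that "this radioligand does show a small degree of sensitivity to the SNP in vivo". The LAB figure rests on "2 men with LAB status".

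Section 7.1 gives the purpose: "This is a Phase 2 pilot study to determine feasibility and preliminary data for a larger study".

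**The concern.** The plan collects a baseline variable that it shows to be related to the outcome, then gives that variable no role in the analysis. Sections 1.1.2 and 1.3.1.1 accept, for other TSPO tracers, that genotype can distort PET results and can be corrected for. Section 1.4.1.3 shows that ER176 keeps some of the same dependence.

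A raw standardized difference suffers in two ways. Genotype variance inflates the denominator. In groups of 15, a chance difference in genotype mix also shifts the numerator: one LAB in place of a HAB moves a group mean by (3.3 − 1.6)/15 = 0.11 mL/cm3.

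The effect size is the main product that this pilot hands to the larger study, so avoidable noise in it carries into that planning. If section 3.3 uses V_T/f_P for its correlations, they are affected in the same way. A genotype adjustment chosen after 11 regions and two measures have been seen would also be less credible than one fixed in advance.

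**Working it through.** **Inputs from the documents.** V_T mean (SD): HAB 3.3 (0.9), MAB 2.9 (0.9), LAB 1.6 (0.5) mL/cm3, from 3, 3 and 2 volunteers (section 1.4.1.3). Target of 15 completers per group (section 3.1.1).

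**Assumptions.** The low-affinity allele frequency q is not in the documents; 0.10 to 0.35 is used, with Hardy-Weinberg proportions (1−q)², 2q(1−q) and q². All 30 subjects are taken to have arterial data. V_T stands in for V_T/f_P.

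**The plan's own figures.** 15/(1 − 0.40) = 25 per group, as stated. The ratios are 3.3/2.9 = 1.14 and 3.3/1.6 = 2.06, against the stated 1.2 and 2.2. They agree only at the edge of rounding, which does not matter here.

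**Variance split.** With genotype proportions f, means m, SDs s and overall mean μ: between = Σf(m−μ)², within = Σf·s². For q = 0.20:
- f = 0.64, 0.32, 0.04 and μ = 3.104
- between = 0.64(0.196)² + 0.32(0.204)² + 0.04(1.504)² = 0.128
- within = 0.96(0.81) + 0.04(0.25) = 0.788
- genotype share = 0.128/(0.128 + 0.788) = 14%
- raw/adjusted effect size = √(0.788/0.916) = 0.93
- sample-size ratio = 0.916/0.788 = 1.16
- SD of the group difference from chance imbalance = √(2 × 0.128/15) = 0.13

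| Quantity | q = 0.10 | 0.20 | 0.30 | 0.35 |
|---|---|---|---|---|
| Between-genotype variance | 0.050 | 0.128 | 0.224 | 0.275 |
| Within-genotype variance | 0.804 | 0.788 | 0.760 | 0.741 |
| Genotype share | 6% | 14% | 23% | 27% |
| Raw/adjusted effect size | 0.97 | 0.93 | 0.88 | 0.85 |
| Sample-size ratio | 1.06 | 1.16 | 1.30 | 1.37 |
| Chance-imbalance SD (mL/cm3) | 0.08 | 0.13 | 0.17 | 0.19 |
| Expected LABs among 30 (30q²) | 0.3 | 1.2 | 2.7 | 3.7 |
| Chance of no LAB, (1−q²)^30 | 74% | 29% | 6% | 2% |
| Mean 95% CI half-width, raw | 0.685 | 0.709 | 0.737 | 0.747 |
| Same, genotype as a factor | 0.685 | 0.685 | 0.680 | 0.668 |

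The half-widths (mL/cm3) are means over 8,000 simulated 15-versus-15 trials per frequency.

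**Without LABs.** Using HABs and MABs only, the raw/adjusted ratio is 0.99 to 0.98, a sample-size ratio of 1.03 to 1.05. LABs drive most of the gain.

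**Cost if genotype had no effect.** At an assumed effect size of 0.8 and two-sided 0.05, simulated power falls by 1 to 2 points with genotype as an allele count and by 2 to 3 points as a factor. With a genotype effect present, type I error after adjustment stays near 5% (4.8 to 5.6%).

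**SUVR.** From V_T and BP_ND in section 1.4.1.3, V_ND = V_T/(1 + BP_ND) = 3.3/5.2 = 0.63 in HABs and 1.6/2.4 = 0.67 in LABs, so specific V_T is 2.67 and 0.93. A 20% rise in specific binding adds 0.53 or 0.19 mL/cm3. If target and cerebellum start equal, the baseline ratio is 1 in both genotypes, so the shift in level cancels. The ratio then rises by 0.53/3.3 = 16% in HABs or 0.19/1.6 = 12% in LABs.

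**The case against.** The strongest objection is that the benefit is uncertain and may be small. The genotype means come from eight volunteers aged 32 ± 9. Using the stated SDs, the pooled-t 95% interval is 1.7 ± 2.3 for HAB minus LAB and 0.4 ± 2.0 for HAB minus MAB; both include zero. If few LABs enrol, adjustment gains almost nothing. The study claims no power, and the effect size is descriptive. At an assumed effect size of 0.8 with 15 per group, its 95% interval is about ± 0.74, while the raw/adjusted ratios would move it by only 0.02 to 0.12. Genotype stays in the dataset, so an adjusted value could be computed later.

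Much of this stands as a limit on size. The variance shares are approximate. The sample-size ratios apply only if the later study will itself adjust; for an unadjusted study the raw value is the right planning input. The cancellation in SUVR is reasoned, not shown by data: section 1.4.1.3 reports HAB regional V_T from 3.2 to 4.3, so regions do not start equal. Coding also matters. At q = 0.20 there is a 66% chance of at most one LAB among 30, and a lone LAB fitted as its own category contributes nothing to the group comparison.

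None of this favours leaving genotype out. The direction of the effect is the protocol's own finding in all regions, the worst-case cost is a few power points, and the raw value can still be reported.

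**Conclusion.** The concern holds. The primary V_T/f_P effect size has no genotype term, the genotype will be in hand, and the protocol's own figures show about a 2-fold HAB to LAB difference in V_T (1.1- to 1.2-fold for HAB to MAB). Over the assumed allele frequencies, the raw effect size understates the adjusted one by 3 to 15%. The mean interval half-width improves by nothing at 0.10 and by about 11% at 0.35 (0.747 to 0.668). Scans without arterial sampling, which section 3.1.3 allows, would lower n and make the degrees of freedom slightly more costly. There is high confidence that the term is missing and cheap to add, and much less in the exact gain. The change should be made, but the study is not invalid without it.

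**What to change.** In sections 3.2 and 7.2, make the primary V_T/f_P comparison in each region a linear model on group plus rs6971 genotype. Report the adjusted group difference divided by the residual SD, with a 95% confidence interval. Beside it, give the raw effect size, with its SD defined, and the genotype counts by group. The two effect sizes use different SDs and should be labelled accordingly.

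State the genotype coding in advance. An allele count (one degree of freedom) performed about as well as a three-level factor in simulation and is safer if few LABs enrol. Add a sensitivity analysis without LABs, because their SD is smaller and the same proportional rise in TSPO adds less V_T in them.

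In section 3.3, name the binding measure and use genotype-adjusted correlations where it is V_T/f_P. For SUVR, present genotype adjustment only as a secondary check.

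The cost is a few sentences in three sections and one or two of 28 degrees of freedom. No new data, subjects or procedures are needed.

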3.1 General Design

3.1.1. Subject recruitment and screening procedures

Men and women age 50 and older will be recruited from the Columbia Doctors Aging and Dementia clinic, the CUMC Alzheimer's Disease Research Center (ADRC), [name] Questionable Dementia 2 (QD2) cohort, and the CUMC Washington Heights-

Inwood Community Aging Project (known locally as WHICAP, R01 AG037212, PI [name]). Participants may also co-enroll from the cognitive aging studies of [name] (protocol AAAO9758) and [name] (protocols AAAI2752, AAAQ8249, and AAAQ8096), and from CUMC protocols AAAO1151, AAAQ7868, and AAAR4352 (PI = [name]). Participants may also self-refer as this study will be registered on clinicaltrials.gov. Informed consent will be obtained prior to study enrollment.

For subjects with cognitive impairment, prior to obtaining informed consent, a licensed physician who is not listed as personnel on this protocol will determine whether the subjects has capacity to provide their own consent. If the subject lacks consent, a legally authorized representative will be required to provide consent for the subject. Only subjects who can provide an understanding of the study procedures, particularly of the risk of pain associated with the arterial catheter placement, by providing verbal assent, may be enrolled via the surrogate consent process. Subjects who are unable to provide meaningful assent will not be enrolled into the study.

Up to 50 subjects will undergo screening including history, physical examination, routine laboratory studies, neuropsychological testing, brain MRI, and amyloid PET imaging.

If any of the above screening procedures have been performed within one year of the ¹¹C-ER176 PET scan visit, then those procedures will not need to be repeated under this protocol. Rather the previously obtained results will be used.

Subjects will be categorized as either amyloid-positive or amyloid-negative on PET. Subjects will be identified as either cognitively normal or cognitively impaired in consensus conference. Subjects must have Clinical Dementia Rating scale score of 0.5 or above and meet clinical criteria for either amnestic MCI (single or multiple-domain)[25] or Alzheimer's disease[26] to be included in the cognitively impaired category. Of the screened subjects, only amyloid-positive patients and amyloid-negative controls will undergo ¹¹C-ER176 PET.

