3.1.2 Neuropsychological testing

The diagnosis of MCI or AD will be based on updated criteria[25, 26]. The neuropsychological test battery will include the following tests: the Mini-Mental State Examination, Selective Reminding Test, Benson Complex Figure Copy and Recall, MINT, Rosen Drawing Test, single word and sentence repetition from the NACC FTD module,

Geriatric Depression Scale (15 items), Trail Making Tests A and B, and Verbal Fluency (CFL, and Animals). Raw scores and demographically corrected T-scores (age, years of education, sex, and ethnicity) will be determined.

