3.1.4 Image processing

FreeSurfer (http://surfer.nmr.mgh.harvard.edu/), the MRI software package comprising a suite of automated tools for segmentation, reconstruction, and derivation of regional volumes and surface-based rendering, will be used for derivation of regions-of-interest (ROIs). Eleven ROIs will be extracted from the structural T1 image: entorhinal cortex, hippocampus, inferior temporal cortex, combined superior and middle temporal cortex, superior parietal lobule, inferior parietal lobule, precuneus, occipital cortex, prefrontal cortex, striatum, and thalamus. Age-adjusted hippocampal volumes will be used to define the presence or absence of neurodegeneration[28]. A single static ¹⁸F-florbetaben image acquired 50-70 min post-injection will be read by a trained investigator blinded to the subject's diagnosis ([name]). A visual binary read (positive or negative) will be determined according to criteria established by Piramal imaging to stratify subjects as amyloid-positive or amyloid-negative.

¹¹C-ER176 PET images will be analyzed using Freesurfer. ROIs will be applied to coregistered PET images to generate time-activity curves. The metabolite-corrected plasma activity curve will be used to estimate rate constants using the one- and two-tissue compartment models using PMOD software. The total distribution volume will be calculated from the resulting rate constants.

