4.1 Inclusion Criteria

- 1. Age 50 and older
- 2. Meet criteria for either a) amnestic mild cognitive impairment (single or mixed domain) or Alzheimer's disease, or b) have no cognitive impairment, based on history, exam, and neuropsychological testing.
- 3. Subjects unable to provide informed consent must have a surrogate decision maker
- 4. Written and oral fluency in English
- 5. Able to participate in all scheduled evaluations and to complete all required tests and procedures.
- 6. In the opinion of the investigator, the subject must be considered likely to comply with the study protocol and to have a high probability of completing the study.

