7.3 Subject Population(s) for Analysis

Subjects will be elders age 50 and older with normal cognition, mild cognitive impairment, or AD.

8 Safety and Adverse Events

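### The primary patient-control effect size is not adjusted for TSPO genotype, age or sex, although the groups are not randomised; a linear model on data already collected would be a cheap improvement

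*Combined protocol and SAP*

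**What the plan says.** Section 3.2 (Primary Study Endpoints) and section 7.2 (Statistical Methods) use the same sentence for the patient-control comparison: "Effect size will be calculated for different regions as the difference in means (AD vs. controls) divided by the standard deviation". It applies to two outcomes: V_T/f_P, and SUVR with the cerebellum as pseudo-reference region. Neither section names a covariate, or says which standard deviation is meant.

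The groups are not randomised. Section 3.1.1 states: "Subjects will be identified as either cognitively normal or cognitively impaired in consensus conference". Only amyloid-positive patients and amyloid-negative controls go on to the ER176 scan, with a target of 15 completers in each group. Section 5.3, on assignment to groups, reads N/A. The demographic rules are "Age 50 and older" (section 4.1) and "Men and women age 50 and older will be recruited" (section 3.1.1). Section 7.3 describes the analysis population in the same terms. No section matches, stratifies or frequency-balances on age, sex or genotype.

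Demographic correction does appear for other measures. For cognition, section 3.1.2 says "Raw scores and demographically corrected T-scores (age, years of education, sex, and ethnicity) will be determined". For MRI, section 3.1.4 says "Age-adjusted hippocampal volumes will be used to define the presence or absence of neurodegeneration". TSPO genotype is determined in all subjects (section 3.1.1), and section 1.1.2 says that genotype correction can be applied to PET data. Sections 3.2 and 7.2 do not take this up.

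**The concern.** In a non-randomised comparison, a raw difference in means mixes the disease effect with the effect of any other determinant of binding that is distributed differently in the two groups. Nothing in the design makes patients and controls alike in age, sex or genotype, and nothing in the analysis allows for a difference.

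What is at stake is the estimate, because section 7.1 presents the study as a pilot that supplies preliminary data for a larger one. On assumed values, take a true effect of 0.50, a within-group age-binding correlation of 0.3 and an age gap of 0.5 SD. The raw effect size would centre on 0.50 + 0.3 × 0.5 = 0.65. A later two-group t-test planned on 0.65 (80% power, two-sided 5%) would have 39 per group, where 64 are needed for 0.50. With the opposite sign, a real signal would be partly hidden.

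**Working it through.** **The plan's own figure.** The only derivable number is the screening target: 30/(1 − 0.40) = 50, or 15/(1 − 0.40) = 25 per group. Both reproduce exactly. No alpha, power or assumed effect is stated.

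**Sampling error, for scale.** With 15 per group, the standard error of the standardised difference near zero is √(1/15 + 1/15) = 0.365, or about 0.37.

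**Genotype (relation given in the documents).** Section 1.4.1.3 reports whole-brain V_T of 3.3 ± 0.9 in high affinity binders (n = 3), 2.9 ± 0.9 in mixed (n = 3) and 1.6 ± 0.5 in low (n = 2).
- In units of 0.9: high minus mixed = (3.3 − 2.9)/0.9 = 0.44; high minus low = (3.3 − 1.6)/0.9 = 1.89.
- Assume that 3 of 15 subjects (0.20) differ in genotype between the groups. The shift is 0.44 × 0.20 = 0.09 for high against mixed, and 1.89 × 0.20 = 0.38 for high against low.
- Limits: eight healthy volunteers with mean age 32, V_T not divided by f_P, and a within-genotype SD. The protocol gives no genotype frequencies for the study population and no reason to expect them to differ by diagnosis.

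**Age (no relation given, so assumed).** Shift in effect size = r × D, where r is the within-group correlation of age with binding and D the gap in mean age in SD units.

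| r | D = 0.25 | D = 0.5 | D = 0.75 | D = 1.0 |
|---|---|---|---|---|
| 0 | 0 | 0 | 0 | 0 |
| 0.1 | 0.03 | 0.05 | 0.08 | 0.10 |
| 0.2 | 0.05 | 0.10 | 0.15 | 0.20 |
| 0.3 | 0.08 | 0.15 | 0.23 | 0.30 |
| 0.4 | 0.10 | 0.20 | 0.30 | 0.40 |

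**Sex (no relation given, so assumed).** Shift = sex effect in SD units × difference in proportions. Sex effects of 0.2 to 0.8 SD with a difference of 3 of 15 give 0.2 × 0.20 = 0.04 to 0.8 × 0.20 = 0.16.

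**Cost of adjusting.**
- Degrees of freedom: 30 − (1 intercept + 1 group + 2 genotype + 1 age + 1 sex) = 24, against 28 unadjusted.
- Standard error with age alone as covariate and gap D: factor √[(1 − r²)(1 + D²/4)]. For D = 0.5 this is 1.03 at r = 0 and 0.98 at r = 0.3. For D = 1.0 it is 1.12 and 1.07.
- Standard error with all four covariate terms, when groups differ only by chance: expected variance factor about 1 + 4/(28 − 4 − 1) = 27/23 = 1.17, so about 1.08 on the standard error if no covariate is related to binding. Adjustment gains precision once the covariates together explain more than 4/27, about 15%, of the within-group variance.

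**The case against.** Several stronger statements are tempting and should not be made.

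- **Patients and controls come from different sources.** Sections 3.1.1 and 4.3 give one joint recruitment list and assign no source to either group. Different sourcing is possible, but it is an inference.
- **Any age or sex imbalance passes straight into the result.** It does so only if the variable is related to binding. At r = 0 the shift is zero, and the documents give no age or sex relation. For SUVR, an effect proportional in target and cerebellum would largely cancel.
- **Chance makes bias likely.** If both groups came from one population (half female), an age gap above 0.5 SD would occur with probability 0.17 and a sex difference of 3 or more of 15 with probability 0.36. Those figures are right, but in that setting the raw estimator is unbiased and the imbalance is already part of the 0.37. They support adjusting for precision and for reading the one realised sample; they are not a probability of bias.
- **Error rates are inflated.** Sections 3.2 and 7.2 plan no significance test, and section 7.1 claims no power.
- **The plan contradicts itself by adjusting elsewhere.** The T-scores support diagnosis, and the age-adjusted hippocampal volume defines neurodegeneration status. These are classification steps and do not oblige the PET comparison to be adjusted.

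The plan does not forbid an adjusted analysis either, so the gap is one of prespecification. Most of the assumed range also lies below the sampling error.

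What survives is that the primary comparison between non-randomised groups names no covariate, including the one that the protocol itself shows to affect binding. A systematic difference, if present, would not shrink with more subjects recruited in the same way.

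**Conclusion.** The point holds as a cheap improvement. The missing adjustment is certain from sections 3.2 and 7.2; the size of its consequence is not.

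Bias needs both a relation with binding and a difference between the groups. The documents establish the first for genotype only, and the second for none of the three variables. For genotype, an assumed difference of 3 of 15 subjects gives about 0.09 (high against mixed) to 0.38 (high against low), from eight volunteers' V_T. For age the range is about 0.03 to 0.40, and for sex 0.04 to 0.16, wholly on assumed relations and gaps. The direction is open. V_T/f_P has no reference region to cancel a proportional effect; SUVR may be largely protected from one.

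The documents do not show that the planned effect size will be biased. They show that the plan has no prespecified way to tell a disease difference from a difference in genotype, age or sex, although genotype is determined for every subject and the demographic T-score correction already requires age and sex.

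**What to change.** In sections 3.2 and 7.2, estimate the patient-control difference in regional V_T/f_P and in SUVR from a linear model on group, TSPO genotype (three categories), age and sex. Report the adjusted difference in native units and as an effect size, each with a 95% confidence interval, and show the raw effect size alongside. State which SD is the divisor: a residual SD with genotype, age and sex removed puts the adjusted effect size on a different scale from the raw one, which is why the native-unit difference is needed as well.

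Cost: wording only, with no new data or visits. The covariates take four degrees of freedom, leaving about 24. Section 3.1.3 allows some scans without arterial catheterisation, so V_T/f_P may have fewer. If the covariates prove unrelated to binding, the standard error is slightly larger, by roughly 8% on the approximation above.
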